### 8.6.1. Prediction models

Logistic regression analysis will be used to evaluate if recovery at 1 month follow-up can predict recovery at 12 months follow-up. Recovery will be defined as HB=1 and SB=100 at 12 months.

Multivariate models will also be performed with 1 month HB/SB scale and baseline variables. We will test if any baseline variables are independently significant together with the scale (HB/SB) at 1-month, and if they increase the predictive ability in the model.

Results will be presented as p-values, odds ratio and 95% CI. To evaluate the predictive ability, ROC curves will be constructed and number of correct classified observations will be presented together with AUC and sensitivity and specificity at the optimal cut-point.

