13.2 STATISTICAL ANALYSIS

The statistical methods will be described in detail in a statistical analysis plan (SAP) that will be finalized and approved before data base lock is performed. Statistical testing may be undertaken for hypothesis generating purposes, using two-sided tests and 5% alpha level, unless otherwise stated.

Data will be presented by treatment group (prednisolone/placebo). Graphical methods may be used wherever it is regarded as appropriate.

The last pre-administration observation will be used as the baseline value for calculating post-administration changes from baseline. All data obtained on the CRF Protocol version 2.3_2021-06-04

and entered into the database will be provided in separate data listings showing individual subject values. Tabulations of summary statistics, graphical presentations, and listings will be performed by the UCR statistician. All statistical calculations will be performed using SAS[®] version 9.4 or later (SAS Institute Inc., Cary, NC, USA) or SPSS statistics, version 21 (IBM Corporation, USA).

Intention-to-treat will be applied when analyzing results from the primary outcome. Comparisons between groups for dichotomous endpoints (recovery/no recovery) will be performed using Fisher's exact test and for categorical endpoints (scale) using Mann-Whitney U-test. For correlations between scales, Pearson's correlation test, or Cohen's kappa if appropriate, will be used. When predicting recovery at 1 month to 12 months, diagnostic performance will be calculated on recovery defined as House-Brackmann grade 1. Analysis of early predictors will be performed to understand variance of subgroups. Furthermore, logistic regression analysis will be used to evaluate recovery in relation to baseline data.

Study patients that have been screened but not received any study medication, will be considered as screen failures and will not be included in the study database.

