###### 5.1.2. Secondary Objective(s)

The secondary objectives are:

- to evaluate the total recovery rate at 1 month as compared to the total recovery rate at 12 months, in order to evaluate if prediction of recovery at 1 month is feasible and/or useful in children with acute facial nerve palsy
- to evaluate subjective symptoms and influence in daily life in children with acute facial nerve palsy
- to evaluate the safety profile for cortisone in children with acute facial nerve palsy

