## 12. Description of Derived Variables

Duration of AE: stop date minus onset date expressed in days

Variable	Algorithm in words	SAS Variable name
Complete recovery of palsy at month 1 according to SB scale	Healed (1) if sunnybrook scale at month 1 is 100. If sunnybrook at month 1 $\leq$ 99 then patients are considered as not healed (0)	Month1_SB_healed
Complete recovery of palsy at month 12 according to SB scale	Healed (1) if sunnybrook scale at Month 12 visit is 100. If sunnybrook at Month 12 visit $\leq$ 99 then patients are considered as not healed (0)	Month12_SB_ghealed
Complete recovery of palsy at month 1 according to HB scale	Healed (1) if HB scale at Month 1 visit =1. If HB scale at Month 1 visit >1 then patients are considered as not healed (0)	Month1_HB_healed
Complete recovery of palsy at month 12 according to HB scale	Healed (1) if HB scale at Month 12 visit =1. If HB scale at Month 12 visit >1 then patients are considered as not healed (0)	Month12_HB_healed
Compliance (%)	Compliance in % = (total number of capsules (10) minus Number of capsules remaining) * 100/10 (0% - 100%)	Compliance_pct

FaCE scale (Total score will be used)

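### SAP 8.6.1 tests its multivariable prediction models and its data-chosen cut-point in the same children used to build them, so those figures will on average be too favourable

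*SAP*

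**What the plan says.** SAP 5.1.2 makes 1-month prediction a secondary objective, "in order to evaluate if prediction of recovery at 1 month is feasible and/or useful". SAP 8.6.1 plans two kinds of analysis.

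- **A yes/no predictor.** "Logistic regression analysis will be used to evaluate if recovery at 1 month follow-up can predict recovery at 12 months follow-up". SAP section 12 fixes 1-month recovery in advance: "Healed (1) if HB scale at Month 1 visit =1" for House-Brackmann and "Healed (1) if sunnybrook scale at month 1 is 100" for Sunnybrook. Protocol 13.2 agrees for House-Brackmann: "diagnostic performance will be calculated on recovery defined as House-Brackmann grade 1".
- **Multivariable models.** "Multivariate models will also be performed with 1 month HB/SB scale and baseline variables". The next sentence adds: "We will test if any baseline variables are independently significant together with the scale (HB/SB) at 1-month", and asks whether such variables improve prediction.

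For results, 8.6.1 promises odds ratios with intervals, ROC curves, and this: "number of correct classified observations will be presented together with AUC and sensitivity and specificity at the optimal cut-point". The baseline variables are not listed or counted, and the criterion that makes a cut-point optimal is not given. No bootstrap, cross-validation, split sample, shrinkage or external data set appears in either document. SAP 8.9 plans further logistic prediction by diagnosis, treatment, age group and gender, and refers to 8.6.1 for presentation.

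**The concern.** A logistic model adapts to chance features of the data it is fitted to, and a cut-point picked from a ROC curve adapts to that curve. Performance measured in the same children is therefore apparent performance, which on average exceeds what new children would show. The gap grows with more fitted variables and fewer non-recovered children.

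These are the figures that will answer whether 1-month prediction is useful. Uncorrected, they can make worthless baseline variables seem to add discrimination, and can present a Sunnybrook threshold as more sensitive than a clinic would find it.

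**Working it through.** **Inputs from the documents**

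- SAP section 9: 80% versus 90% recovery, two-sided 5% level, 80% power, 430 needed, 10% loss, 500 included, 250 per group.
- Protocol section 5: 35% of paediatric cases idiopathic.
- SAP 8.8: complete-case analysis for secondary analyses.

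**Reproducing the plan's figure.** The normal approximation gives 199 per arm (398) without continuity correction and 219 per arm (438) with it. Fisher's exact test at 215 per arm has power 0.803, so 430 is reproduced. Allowing for loss, 430 / 0.90 = 478, which the SAP rounds up to 500.

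**Data available for prediction**

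- Evaluable: 500 × 0.90 = 450.
- Pooled non-recovery: (20% + 10%) / 2 = 15%, so 450 × 0.15 ≈ 68 children. At 10% and 20% this is 45 and 90.
- Idiopathic subgroup: 450 × 0.35 ≈ 158 children, of whom 158 × 0.15 ≈ 24 not recovered.

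**Assumptions not in the documents**

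- The underlying 1-month score has a true AUC of 0.7, 0.8 or 0.9.
- Zero, 5 or 10 baseline variables of no true value are added.
- Optimal means maximum Youden index (sensitivity + specificity − 1).
- Non-recovery is 15%, with 10% and 20% also run at AUC 0.8.

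**Method.** The score is normal with unit variance in each outcome group, and the means differ by √2 × Φ⁻¹(AUC). It is grouped into six grades for House-Brackmann, or rounded and truncated for Sunnybrook. For each of 300 simulated trials, the model is fitted, the cut-point chosen, and both applied to 20,000 new children. Optimism is the apparent value minus the new-children value.

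| Predictor, n = 450 | Optimism in AUC | Optimism in sensitivity + specificity |
|---|---|---|
| 1-month recovery, yes/no | about 0 | −0.003 to +0.002 |
| House-Brackmann grade alone | about 0 | 0.005 to 0.023 |
| Sunnybrook alone | about 0 | 0.037 to 0.052 |
| Sunnybrook + 5 to 10 variables | 0.012 to 0.067 | 0.058 to 0.144 |
| Sunnybrook + 10 candidates, kept only if p<0.05 | 0.007 to 0.021 | 0.049 to 0.075 |

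A separately written simulation at 15% non-recovery gave:

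- one continuous scale: 0.04 to 0.06 in sensitivity plus specificity;
- 5 to 10 added variables: 0.01 to 0.06 in AUC and 0.06 to 0.15 in sensitivity plus specificity;
- only p<0.05 variables kept: 0.004 to 0.011 and 0.05 to 0.08.

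**Worked example (true AUC 0.8, 15% non-recovery)**

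- Sunnybrook alone: apparent 0.755 + 0.724 = 1.479; new children 0.715 + 0.721 = 1.436; difference 0.043.
- Sunnybrook + 10 variables: apparent 0.743 + 0.765 = 1.508; new children 0.651 + 0.750 = 1.401; difference 0.107. AUC falls from 0.808 to 0.764.
- Proportion correctly classified at that cut-point, for the 10-variable model: apparent 0.15 × 0.743 + 0.85 × 0.765 = 0.762; new children 0.15 × 0.651 + 0.85 × 0.750 = 0.735. The difference of 0.027 is about 12 of 450 children.

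**Idiopathic subgroup (158 children, true AUC 0.8).** Sunnybrook alone: 0.079 in sensitivity plus specificity. With 10 variables: 0.107 in AUC and 0.248 in sensitivity plus specificity.

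**How often.** Apparent sensitivity plus specificity exceeded the new-children value in about 78% to 81% of simulated trials for Sunnybrook alone, and in 89% to 100% with 5 to 10 fitted variables.

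**The case against.** The strongest reply is that the main question is already protected. The leading analysis in 8.6.1 uses 1-month recovery as a yes/no predictor with cuts fixed in advance, so no cut-point is left to choose. That stands: a reader might infer that the whole answer on 1-month prediction is biased, and the documents do not support this.

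Three other inferences also go too far.

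- **That choosing a cut-point inflates the AUC.** AUC is computed over all cut-points. Optimism in AUC comes only from fitting several variables.
- **That the SAP keeps only significant variables.** Section 8.6.1 says that they will be tested and states no retention rule. If such a rule were used, optimism in AUC would be smaller than with all 10 variables fitted, though not zero.
- **That the figures will be too favourable in every case.** The bias is an average; a single trial can go the other way.

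It can also be said that this is a secondary analysis, that Protocol 13.2 allows testing for hypothesis generation, and that no prediction rule for clinical use is promised. This limits the importance of the point: the primary comparison is untouched. It does not make apparent figures the right ones to report on a stated objective. The output shells in SAP Appendix 1 are not among the documents and might say more, but a validation method belongs in 8.6.1.

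**Conclusion.** The point holds for two things: the multivariable models, and sensitivity, specificity and correct classification at a data-chosen cut-point. It does not extend to the yes/no predictor or to the AUC of House-Brackmann or Sunnybrook alone.

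Taking both simulations together, optimism in sensitivity plus specificity is about 0.04 to 0.06 for Sunnybrook alone and about 0.02 or less for House-Brackmann alone. With 5 to 10 uninformative variables fitted, it is about 0.06 to 0.15, with 0.01 to 0.07 in AUC. If only p<0.05 variables are kept, the figures are about 0.05 to 0.08 and 0.004 to 0.02. The bias is larger within the SAP 8.9 subgroups if the models are fitted separately there, which 8.9 leaves unclear.

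The sizes depend on the assumed true AUC, non-recovery rate, number and worth of the variables, and Youden criterion. The direction does not. For a single scale the effect is modest; for the multivariable models it could change the conclusion on whether baseline variables help.

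**What to change.** In SAP 8.6.1:

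1. Make sensitivity and specificity at the fixed 1-month cuts (House-Brackmann 1, Sunnybrook 100) the main prediction result.
2. List the candidate baseline variables and state any selection rule.
3. Define the optimal cut-point, for example as the maximum Youden index, and state the threshold used to count correct classifications.
4. Report bootstrap optimism-corrected AUC, sensitivity, specificity and correct classification (for example 500 resamples) beside the apparent values. Repeat any variable selection and the cut-point choice in every resample.
5. Judge the added value of baseline variables by the corrected change in AUC.
6. Label any data-chosen cut-point exploratory.

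Section 8.9 should say whether the models are refitted within subgroups; if so, the same correction applies there. Items 2 and 3 are needed for item 4 to be programmable. No new data are required and the primary analysis is unchanged. The cost is a little more programming and slightly less favourable reported figures.

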### 8.6.2. Correlation and agreement

For correlations between degree of recovery measured by physician assessed grading (House-Brackmann or Sunnybrook) and child/parent assessed quality-of-life measures at 1 and 12 months follow-up visits, Spearman's correlation will be used.

QoL will be measured with:

- Facial Clinimetric Evaluation (FaCE) scale (0-100)
- Facial Disability Index (FDI) scale, as two separate subscales Physical function (0-100) and Social/Wellbeing (0-100).
- Synkinesis Assessment Questionnaire (SAQ) scale (0-100)

Agreement between House-Brackmann and Sunnybrook grading scale will be assessed using Cohen's kappa.

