###### 5.2.2. Primary outcome measure

The physician performed House-Brackmann grading scale (1 is normal and 6 is total loss of function) is chosen as primary outcome measure in the FACE study, since it is a valid and easy to perform grading scale for evaluation of facial nerve function and it has most

frequently been used in previous studies. The primary outcome measure (recovery) is defined as House-Brackmann grade 1 at 12 months follow-up. The time point for the primary outcome is chosen as no further spontaneous recovery of the facial nerve function is expected after 12 months and it is used in previous studies.

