#### 5.2.3. Secondary Endpoint(s)

Secondary endpoints are:

- the total recovery rate at 12 months follow-up in the two treatment groups measured with the Sunnybrook scale.
- The Sunnybrook scale (100 is normal function and 0 is total loss of function) is another objective scale for grading the facial nerve function. It will be used as secondary outcome measure. It is validated for children, easy to perform and has been used in previous studies. It correlates well to the House-Brackmann scale and has been shown to be useful for prediction of recovery in adult patients.
- the agreement between the two grading scales for facial impairment (House-Brackmann and Sunnybrook), in order to decide which grading scale has the most preferable utility and should be recommended in pediatric patients
- the total recovery rate at 1 month follow-up as compared to the total recovery rate at 12 months follow-up, measured with Sunnybrook and House-Brackmann scale (prediction).
- quality of daily life at 1 and 12 months follow-up measured with the Facial Clinimetric Evaluation (FaCE) scale and the Facial Disability Index (FDI) and at the 12 months measured with the Synkinesis Assessment Questionnaire (SAQ) and to correlate them to the physician assessed House-Brackmann and Sunnybrook grading scales .
- number of Adverse Events possibly or probably related to the study drug during the 12 months follow-up.

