#### 5.2.4. Secondary outcome measures

The physician performed Sunnybrook grading scale (100 is normal and 0 is total loss of function) is chosen as secondary outcome measure as it correlates well to the House-Brackmann scale in adult patients, is easy to perform and evaluates facial function in rest and activity. Both the House-Brackmann and the Sunnybrook grading scale are included in order to be able to evaluate agreement between them, and to decide which one has the best most preferable utility and thus should be recommended for evaluation of facial nerve palsy in children. Sunnybrook has also been used for prediction of prognosis in adult patients and will now be evaluated for prediction of recovery in pediatric patients.

Three validated child/parent assessed instruments for disease specific quality-of-life are chosen as additional secondary outcome measures for patient/parent reported outcome measures (PROMs), in order to examine and better understand facial disability (18-21).

The Facial disability index (FDI) consists of 10 different items (6 is full satisfaction, 1 is no satisfaction) divided into two domains; physical function (with composite score of -25 – 100) and social/well-being function (with a composite score of 0-100) (18).

The Facial Clinimetric Evaluation Scale (FaCE scale) includes 15 items (5 is full satisfaction, 1 is no satisfaction) in six domains and a total composite score of 0-100.

The Synkinesis Assessment Questionnaire (SAQ) includes 9 items concerning defect recovery (1 is full satisfaction, 5 is no satisfaction) and gives composite score of 0-100.

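### Cohen's kappa cannot rank House-Brackmann against Sunnybrook, and the planned results that could inform the choice of scale are neither linked to it nor set up for comparison

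*SAP*

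**What the plan says.** **Purpose.** SAP 5.2.3 lists agreement between the two physician-graded scales as a secondary endpoint, "in order to decide which grading scale has the most preferable utility and should be recommended in pediatric patients". SAP 5.2.4 repeats it: both scales are included so that agreement can be evaluated and "to decide which one has the best most preferable utility and thus should be recommended for evaluation of facial nerve palsy in children". Neither section defines utility or gives a rule for the decision.

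**Method for agreement.** SAP 8.6.2 has one sentence: "Agreement between House-Brackmann and Sunnybrook grading scale will be assessed using Cohen's kappa". It names no categories, weighting or visit.

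**Other results reported by scale.**
- SAP 8.6.1 plans logistic models with the 1-month House-Brackmann or Sunnybrook value, reported with ROC curves, AUC, sensitivity, specificity and correct classification. On the outcome it says "Recovery will be defined as HB=1 and SB=100 at 12 months".
- SAP 8.6.2 plans Spearman correlations of either scale with FaCE, FDI and SAQ.

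**Derived variables.** SAP 12 defines a matching pair of indicators at month 1 and month 12. For month 12 these are "Healed (1) if HB scale at Month 12 visit =1" and "Healed (1) if sunnybrook scale at Month 12 visit is 100".

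**Protocol.** Section 13.2 bases the diagnostic performance of 1-month recovery for 12-month recovery on House-Brackmann grade 1. For the relation between scales it allows Pearson's correlation, or kappa where suitable. SAP 11 declares no change to the planned analysis.

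**The concern.** A choice between two instruments needs an analysis that can come out in favour of one or the other. Kappa cannot: it measures how often two classifications coincide beyond chance and treats them alike. As written it also cannot be computed, because House-Brackmann has six grades and Sunnybrook runs from 0 to 100.

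The analyses that could inform the choice are planned for other aims. With no stated criterion, a recommendation for paediatric practice could rest on whichever per-scale result looks most persuasive once the data are seen. If each scale's AUC is calculated against that scale's own definition of recovery, the two AUCs answer different questions and should not be set side by side.

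**Working it through.** The documents give no target kappa, precision or sample size for agreement, so there is no planned figure to reproduce. The check is whether kappa can carry the decision, and whether the other planned results can.

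**1. Shared categories.** House-Brackmann takes grades 1 to 6 (SAP 5.2.2) and Sunnybrook 0 to 100 (SAP 5.2.4). The only categories the SAP defines for both are grade 1 against above 1, and 100 against 99 or less (SAP 12). Those give a 2x2 table.

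**2. Symmetry.** Kappa = (po − pe)/(1 − pe), where po is observed and pe chance agreement. The counts below are assumptions chosen for illustration.

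| | Sunnybrook 100 | Sunnybrook ≤ 99 | Total |
|---|---|---|---|
| House-Brackmann 1 | 351 | 32 | 383 |
| House-Brackmann > 1 | 0 | 67 | 67 |
| Total | 351 | 99 | 450 |

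- po = (351 + 67)/450 = 0.929
- pe = (383 × 351 + 67 × 99)/450² = 141,066/202,500 = 0.697
- kappa = (0.9289 − 0.6966)/(1 − 0.6966) = 0.766

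Swapping the scales transposes the table. The diagonal and the products of the margins stay the same, so kappa is again 0.766.

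**3. The same table under opposite truths.**
- If Sunnybrook were the truth, House-Brackmann would have sensitivity 351/351 = 1.00 and specificity 67/99 = 0.68.
- If House-Brackmann were the truth, Sunnybrook would have sensitivity 351/383 = 0.92 and specificity 67/67 = 1.00.

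One kappa is compatible with either scale being the correct one.

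**4. Other assumed proportions.** Suppose 85% have House-Brackmann 1 and 75% have Sunnybrook 100, all of the latter also being grade 1. Then po = 0.75 + 0.15 = 0.90, pe = 0.85 × 0.75 + 0.15 × 0.25 = 0.675, and kappa = 0.225/0.325 = 0.69. The value moves with the proportions; the symmetry does not.

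**5. The ROC results.** The outcome sentence in SAP 8.6.1 can be read in at least three ways: each scale against its own 12-month definition, both scales against each definition in turn, or both against a joint definition. Only the last two make the AUCs comparable. Protocol 13.2, with House-Brackmann grade 1 alone, gives one common outcome, but the SAP sentence does not say that it follows it. No test or interval for a difference in AUC is specified.

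**6. The correlations.** SAP 8.6.2 correlates each scale with the same questionnaires, so the results share a target. No difference between the two correlations is planned. It also assigns Spearman to scale against questionnaire only, so the direct correlation between scales that the protocol allowed has no place in the SAP.

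**The case against.** The strongest reply is that the SAP does plan informative results for each scale. AUC, sensitivity and specificity from the 1-month values, and correlations with FaCE, FDI and SAQ, are the sort of evidence on which one would prefer a scale. This stands. A reader might infer that a recommendation would rest on no planned analysis at all; SAP 8.6.1 and 8.6.2 contradict that.

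Second, SAP 5.2.4 separates evaluating agreement from deciding on a scale, and SAP 8.6.2 assigns kappa only to agreement. This is fair for that section, and kappa does serve the agreement part. SAP 5.2.3, however, presents agreement as the means to the decision, and no section assigns the decision another method.

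Third, a reader might infer that each scale will be tested only against itself. The documents do not say so, and Protocol 13.2 points to a single outcome. What remains is that the SAP sentence leaves it open.

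Fourth, a reader might infer that kappa is possible only on healed/not healed. Sunnybrook could be banded, so that is too absolute; but the SAP gives no bands. Conversely, the derived indicators make a binary kappa feasible at once.

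Finally, the output shells in SAP Appendix 1 are not among the documents available here and may specify the kappa table. Some grounds for preferring a scale, such as ease of use, are not statistical.

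**Conclusion.** The point holds in a limited form. Agreement is evaluated in order to choose a scale, and the one method assigned to it cannot favour either scale whatever its value. That follows from the definition of kappa and does not depend on the assumed counts. The results that could inform the choice are planned, but they are not linked to it, no House-Brackmann-versus-Sunnybrook contrast is specified, and the outcome for the ROC analysis is ambiguous between SAP and protocol.

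The illustrative kappas of 0.69 and 0.77 show the symmetry; they do not measure harm. The stronger claim, that the SAP contains nothing bearing on the choice, is not supported. This is a secondary, methodological aim. The primary comparison of prednisolone with placebo is untouched, so the change is worth making but not critical.

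**What to change.** **In SAP 8.6.2.** Run kappa on healed/not healed at months 1 and 12, shown with the 2x2 table, as a description of agreement. Add Spearman's correlation of House-Brackmann grade with Sunnybrook score.

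**For the recommendation.** State in a sentence what utility means, and name the analyses that will inform it:
- Main: a paired comparison (DeLong) of the AUCs of 1-month House-Brackmann and 1-month Sunnybrook in the same children against the same 12-month outcome. Take House-Brackmann grade 1 as the outcome, in line with Protocol 13.2. Repeat with Sunnybrook 100 as sensitivity, because each outcome may favour its own scale. Say beforehand that opposite results mean no preference on predictive grounds.
- Supporting: the difference between the two scales' Spearman correlations with FaCE, FDI and SAQ, with a bootstrap confidence interval. Compare absolute values, since the scales run in opposite directions.

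**In SAP 8.6.1.** Say which 12-month outcome applies to each model.

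**Alternative.** Remove the aim of deciding between the scales from SAP 5.2.3 and 5.2.4 and report agreement descriptively.

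**Cost.** A few lines of SAP text and a few extra secondary analyses on data already collected: kappa with its table at two visits, one correlation between scales, the AUC comparison and its repeat, and the correlation differences. No extra visits or patients are needed.
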